**Additionally:**

- **At SV1 and Randomization/TV 1 (Day 0), post-debridement images are required.**
- **Further, and if the subject is randomized to the Active Treatment cohort, photographs of the PriMatrix product after application are required.**

Ulcer photographs are being obtained for ulcer measurements, documentation, and archival purposes and may also be used in educational and/or marketing materials.

Note: Specific imaging instructions are explained in a separate manual.

## 5.9. Sharp Debridement

Only sharp debridement is permitted in this study and includes debridement of all non-living or contaminated tissue from the wound bed. All callus should be removed, and any undermined or tunneled areas explored to ensure exposure of the full wound bed. Broad area cauterization should be avoided. Anesthetics are permitted during debridement.

**IMPORTANT: Sharp debridement of the study ulcer is required at SV1 and Randomization/TV 1 (Day 0).**

Sharp debridement includes removal of:

- the surrounding callus
- All non-viable tissue, as evidenced by punctate bleeding across the wound bed

At visits other than SV1 and Randomization and if needed, sharp debridement should be performed to:

- Remove callus or devitalized tissue
- Remove infected tissue

Whenever debridement is performed, details of debridement will be captured on the eCRF (i.e., reason(s) for performing debridement, type of debridement performed, and method used for debridement).

### 5.9.1. Debridement Certification

[figure not shown]
Each investigator and sub-investigator who will be debriding subjects for the trial is required to complete debridement certification prior to debriding subjects.

Certification will consist of the investigator providing a photograph of a non-study patient\* they have debrided. This photograph will be evaluated by the Lead investigator or sponsor approved personnel. If debridement is acceptable, the investigator/sub-investigator will receive documentation of approval from the sponsor. If debridement is not acceptable, feedback will be provided to the investigator/sub-investigator and the process will be repeated. This will continue until the debridement technique is satisfactory. Satisfactory verification of training must occur prior to enrollment of first subject.

\* *An exception may be made in the case of an ethics board that does not allow for transmission of images for non-study subjects. In this case, the first study subject debrided by the investigator will serve as the certification subject. If the debridement on this subject is not certified, the subject is screen failed. As above, the process repeats until a sufficiently debrided image is produced.*

The images in figure 2 have been supplied to provide examples of acceptable and unacceptable debridement.

Figure 2: Images of Acceptable Debridement

## 5.10. Ulcer Measurements

### 5.10.1. Computerized Planimetry

Ulcer measurements are required at each visit. The study DFU area will be determined by computerized planimetric analysis of digital photographs using software created by an external vendor.

The software allows the user to capture digital ulcer images and generate area measurements. Data collected by the software will be uploaded to a central server. All ulcer assessment data will be organized as a patient record on a central server and available for review and reporting. To ensure consistency between sites, training for procedures will be provided by a representative from the external vendor or by a trained sponsor representative. A manual containing information regarding how to use the software will be provided to the sites.

In addition, measurements will be performed by the investigator or qualified site staff at each visit.

#### 5.10.2. Ulcer Area Reduction

Percent change in study ulcer area from the post-debridement SV1 to post debridement randomization will be calculated by the imaging vendor using computerized planimetry of images taken of the ulcers.

At the Randomization/TV 1 (Day 0), ulcer area reduction will be used to qualify the subject for randomization and study enrollment. ***The reduction in study ulcer area may not exceed 30% after sharp debridement in order for the subject to be randomized.***

#### 5.11. Standard of Care (Control) Treatment

During the Screening Phase of the study, all subjects will have SOC products applied by the investigative site at the weekly visits. They will be then instructed on how to change their dressings on a daily basis. After randomization, only subjects who are randomized to the SOC cohort will continue daily dressing changes. Those subjects in the Active Treatment cohort will only have their dressings changed weekly at follow-up visits until the investigator determines that their wound has closed. If the wound closes on or before treatment visit 13, offloading (if previously utilized for that subject) will continue *without* dressings during the follow-up period.

##### **Application of the dressings & boot by the Investigator:**

1. Gently remove any dressing previously applied to the wound and clean the area with a gentle cleanser.
2. If appropriate, debridement and hemostasis will be performed. (Note: in this study only sharp debridement will be used)
3. During Screening and for SOC-randomized subjects: Instruct the subject on the proper way to change dressing
  - Inspect the wound and perform study assessments as directed elsewhere
4. Apply normal saline gel to the thickness of a coin.
5. Cover the gel with a foam dressing.
6. Secure the foam dressing with conforming roller gauze.
7. Cover the roller gauze with Coban.
8. For subjects who have ulcers that require offloading, apply the boot.

##### **Daily Changing of the Dressings by the Subject:**

1. Remove boot, if applicable
2. Gently remove dressings
3. Clean the wound with tap water and pat the area dry

4. Inspect the wound
  - a. Subject will contact the site by phone if they believe there is anything wrong with the wound.
5. Apply normal saline gel to the thickness of a coin.
6. Cover the gel with a foam dressing.
7. Secure the dressings with conforming roller gauze.
8. Cover the roller gauze with Coban.
9. For subjects who have ulcers that require offloading, re-apply the boot.

Note: Subjects who use the offloading boot will be instructed that it is to be worn **at all times** except when bathing or sleeping.

#### 5.12. Compliance with Offloading & Dressing Changes

At SV1, and as indicated in Section 5.11 above, subjects will be instructed on the proper use of the off-loading/protective device and in the proper procedures for dressing changes and care as required by the treatment assignment. At SV2 through TV13 and unscheduled visits, the subject will be queried about their compliance with dressing changes and offloading, as prescribed. If subject non-compliance is noted, documentation of the incident will be recorded. If continued non-compliance is detected, the subject may be withdrawn from the study at the discretion of the investigator and/or sponsor.

#### 5.13. Appropriate Off-loading/Protective Device

The off-loading/protective device to be used in this study will be provided by the sponsor through a specific distributor. This off-loading/protective device will be used by all subjects with study ulcers located on the plantar or lateral surfaces of the foot (i.e., any location experiencing weight-bearing or shear forces) throughout the Screening, Treatment and Follow-up phases.

All subjects enrolled in this study are required to use the sponsor-provided off-loading/protective device for the duration of their participation (see Inclusion Criteria 9).

Off-loading devices **MUST** be continually used throughout the entire duration that the subject is enrolled in the study.

Note: If a subject is wheelchair bound, meaning that their primary form of locomotion is in the wheelchair, the offloading boot will not be required. If at any point in time, the subject ceases to be wheelchair bound, they will begin using the offloading boot if necessary.

Subjects with ulcers located on non-weight bearing surfaces (i.e., the dorsum of the foot) may use the provided off-loading boot as a protective device or may use another form of protective foot wear. The off-loading/protective device used will be noted in the eCRF.

Complete compliance information on the use of the off-loading/protective device by the subject will be collected by the study staff at each visit via subject interviews. Off-loading information collected will include type of off-loading/protective device used, number of hours per day that the device was not used since the last study visit and what proportion of that time involved weight-bearing, and any problems or issues with the off-loading/protective device. Subjects will be instructed to wear the off-loading/protective device at all times, except during sleeping, bathing, or showering.

#### 5.14. Concomitant Medications and Non-Study Treatments

Only therapies/medications that may impact healing, are related to AEs (e.g., antibiotics/antimicrobials, surgical excision/amputation) or linked to DM (i.e., insulin and oral hypoglycemics) will be collected. These medications/therapies administered or taken by the subject beginning 28 days prior to signing the ICF and throughout the study will be recorded in the source documents and, for randomized subjects, on the appropriate eCRF. For each medication and non-study treatment, the following will be documented:

- Medication/treatment name (generic name may be used if trade name is unknown)
- Dose, unit, and frequency of dosing (individual dosage, not total daily dose).
- Each new dose of medication should be recorded as a separate entry, with the exception of medications that are given on a sliding scale. For these, it is acceptable to enter the range of the dosage, including the start and stop dates for which the specified dosage range was used.
- Route of dosing
- Indication for use
- The start date
- Whether the medication is ongoing or was discontinued
- The stop date (if medication/therapy is not ongoing)
- Adverse event number (if applicable)

##### 5.14.1. Prohibited Medications and Therapies

The following treatments/medications/procedures are prohibited during the subject participation in this study, beginning with the first Screening Visit (SV1) and should they be medically required, the subject must be discontinued from the study.

To the study ulcer:

- Application of growth factors, engineered tissues or skin substitutes, other than the Active Treatment (PriMatrix), including but not limited to: Regranex® (Smith & Nephew), Dermagraft® (Organogenesis), Apligraf® (Organogenesis), EpiFix (MiMedx), AMNIOEXCEL (Integra), GraftJacket® (KCI, an Acelity Company), OASIS (Smith & Nephew), MatriStem® (ACell), Omnigraft® (Integra)

LifeSciences), or Integra BMWD® (Integra LifeSciences) Enzymatic debriding agents

- Topical Oxygen Therapy
- Negative Pressure Wound therapy

To the subject:

- Systemic investigational treatment/medications
- Dialysis
- Immunosuppressive agents
- Systemic steroids/oral corticosteroids (>25mg/d for >3 days) (**Note:** inhaled steroids are acceptable)
- Autoimmune disease therapies
- Radiation therapy to the foot
- Cytostatic drugs
- Vascular surgery of the affected limb
- Thrombolysis and/or angioplasty

Only dressing materials provided by the sponsor may be used on the target ulcer. Ulcer dressings that have not been provided by the study sponsor for use in the trial may be used on ulcers that are NOT designated as the study ulcer.

## 5.15. Adverse Events

### 5.15.1. Definitions

An adverse event (AE) is defined as any untoward medical occurrence occurring in a clinical trial. An AE does not necessarily have a causal relationship with the device. A device-related AE can be any unfavorable and unintended sign, symptom, or disease temporally associated with the use of a study device, whether or not related to the device.

**For the purposes of this study, only AEs that are possibly, probably, or definitely related to the study ulcer, study treatment, and/or study procedures are to be recorded.** All events starting or worsening beginning at SV2 through Treatment Visit Week 13 and unscheduled visits will be collected. Follow-up treatment and evaluation should continue until the AE has resolved or until 2 weeks after the final visit, whichever occurs first.

AEs not related or unlikely related to the study treatment, study ulcer and/or study procedures are not to be recorded for this study.

A Serious Adverse Event (SAE) is defined as any AE that:

- Results in death

- Is life threatening (the subject is at immediate risk of dying from the adverse experience)
- Requires subject hospitalization or prolongs existing hospitalization
- Results in persistent or significant disability/incapacity
- Is a congenital anomaly/birth defect
- Important medical events that may not result in death, be life-threatening, or require hospitalization may be considered a serious adverse device effect when, based upon appropriate medical judgment, they may jeopardize the subject or subject and may require medical or surgical intervention to prevent one of the outcomes listed in this definition.

For the purposes of this study, only SAEs that are possibly, probably, or definitely related to the study ulcer, study treatment, and/or study procedures are to be recorded. All events starting or worsening after the first randomized treatment through Treatment Visit Week 12 will be collected. Follow-up treatment and evaluation should continue until the SAE has resolved or until 2 weeks after the final visit, whichever occurs first.

SAEs not related or unlikely related to the study treatment, study ulcer and/or study procedures are not to be recorded for this study.

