### 6.2.1. Randomization/TV 1 (Day 0)

1. Review Inclusion and Exclusion criteria for eligibility
  - *Important: The final exclusion criteria will only be determined after debridement and measurement as detailed below in this Section.*
2. Medical Resource Utilization assessment will be performed (see Section 5.3 for specific information on how to perform this assessment).
3. Ask subject about compliance with the treatment during the previous week
4. Perform ulcer assessments
5. Photograph the study ulcer pre-debridement
6. Perform ulcer measurements pre-debridement
7. Assess the ulcer for wound closure status
  - If the wound is closed, the subject is exited at this point; complete the study exit form.
8. Perform sharp debridement of the study ulcer
9. Photograph of the study ulcer post-debridement
10. Perform ulcer measurements post-debridement
11. Document ulcer size reduction
12. Complete the randomization process in the EDC system.
13. Apply either SOC or the Active treatment to the ulcer, depending on the cohort that is assigned during the randomization process (see Section 5.16 for specific application processes)

14. Discuss treatment compliance with the subject
15. If appropriate, apply the off-loading/protective device and discuss compliance with its use
16. Document applicable Concomitant Medications noted by the subject or seen within the subject's medical records (see Section 5.14 for information on which medications require documentation).
17. Document any applicable AEs as noted by the subject or as documented in their medical record (see Section 5.15 for information on which AEs require documentation).

*\* Remember to schedule the next visit for Treatment Visit Week 2, 7±3 days from Randomization/TV 1.*

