#### 6.2.3. Closure Confirmation Visit (7±3 days after ulcer determined to be closed)

Closure Confirmation assessments and procedures are identified in Table 3.

1. Medical Resource Utilization assessment will be performed (see Section 5.4 for specific information on how to perform this assessment).
2. Perform ulcer assessments
3. Photograph the study ulcer
4. Assess the ulcer for wound closure status
5. Document any applicable AEs as noted by the subject or as documented in their medical record (see Section 5.15 for information on which AEs require documentation).

Special Instructions: If the subject returns for the closure confirmation visit AND the ulcer has reopened AND Treatment Visits 12 or 13 has not yet been reached, the subject re-enters the study at the visit after the previously scheduled next visit (e.g., if the ulcer closed at TV9, but at the Confirmation Visit the ulcer is reopen, the subject re-enters at TV11). The subject will then return every 7±3 days for up to 13 weeks or until the ulcer closure is confirmed, whichever occurs first. This process repeats until all treatment visits are used up. If the subject's wound is closed on TV 12 or 13, but is open at the Confirmation Visit they do not re-enter the study and are exited.

*\* Remember to schedule the next Treatment Visit or the 4-Week Follow-Up visit as appropriate.*

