#### 6.2.4. 4-Week Follow-Up Visit (28±3 days after Confirmation Visit)

The 4-week follow-up visit assessments and procedures are identified in Table 3.

1. Perform ulcer assessments
2. Photograph the study ulcer
3. Assess the ulcer for wound closure status

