#### 6.2.5. Unscheduled Visits

IMPORTANT: Unscheduled visits are to ***ONLY*** be used when a subject has an unexpected clinic visit that falls outside the next visit window. If the date of the unexpected visit falls within the window of the next regular visit, the procedures for that visit will be followed.

In the event an unscheduled visit occurs, the following will be occur:

1. Perform ulcer assessments
2. Perform sharp debridement of the study ulcer, if necessary per investigator discretion.
3. Apply either SOC or the Active treatment to the ulcer, depending on the cohort that is assigned during the randomization process (see Section 5.11 or 5.17 for specific application processes of SOC or Active treatment, respectively.).
4. Discuss treatment compliance with the subject
5. If appropriate, apply the off-loading/protective device and discuss compliance with its use
6. Document applicable Concomitant Medications noted by the subject or seen within the subject's medical records (see Section 5.14 for information on which medications require documentation).
7. Document any applicable AEs as noted by the subject or as documented in their medical record (see Section 5.15 for information on which AEs require documentation).

Important: If the Unscheduled Visit occurs between the closure visit and either the Confirmation Visit or the 4-Week follow-up visit, activities 2 through 5 will not be performed. If the wound is open at the follow-up visit, and the subject has not reached their Confirmation Visit, the subject will be re-entered per the Special Instructions in 6.2.3. SOC dressings may be applied until the next Treatment Visit. If the subject is open between the Confirmation Visit and the 4-Week follow up visit, the subject is exited.

Table 3: Schedule of Events

Procedure	Screening Phase		Treatment Phase													Follow-Up Phase		Unscheduled Visit 
	SV 1 -14±3d	SV 2 -7±3d	Randomiza- tion/ TV  1 (Day 0)	TV 2 7±3d	TV 3 14±3d	TV 4 21±3d	TV 5 28±3d	TV 6 35±3d	TV 7 42±3d	TV 8 49±3d	TV 9 56±3d	TV 10 63±3d	TV 11 70±3d	TV 12 77±3d	TV 13 84±3d	Conf Visit 7±3d After Closure	4-Week 28±3d After Confirm.	
Inf. Consent/HIPAA	X																	
Inclusion/Exclusion	X	X	X															
MRU Assessment		X	X	X	X	X	X	X	X	X	X	X	X	X	X	X		
Demographics	X																	
Medical History	X																	
Physical Exam	X																	
Vascular Perfusion	X																	
Ulcer Assessments 	X	X	X	X	X	X	X	X	X	X	X	X	X	X	X	X	X	X

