Ulcer Photography	X 	X 	X 	X 	X 	X 	X 	X 	X 	X 	X 	X 	X 	X 	X 	X 	X 	
Ulcer Debridement	X	X 	X	X 	X 	X 	X 	X 	X 	X 	X 	X 	X 	X 				X 
Ulcer Measurement	X	X	X	X	X	X	X	X	X	X	X	X	X	X	X			
Control Treatment	X	X	X 	X 	X 	X 	X 	X 	X 	X 	X 	X 	X 	X 				X 
Treatment Compliance	X	X	X	X	X	X	X	X	X	X	X	X	X	X	X			X
Offloading 	X	X	X	X	X	X	X	X	X	X	X	X	X	X				X
Concomitant Meds	X	X	X	X	X	X	X	X	X	X	X	X	X	X	X			X
Adverse Events		X	X	X	X	X	X	X	X	X	X	X	X	X	X	X	X	X
Ulcer Size Reduction			X															
Randomization			X															
Active Treatment			X 	X 	X 	X 	X 	X 	X 	X 	X 	X 	X 	X 				X 
Closure Assessment			X	X	X	X	X	X	X	X	X	X	X	X	X 	X	X	

 Only to be used for a visit that falls out of range of one of the other visit windows. If the proposed Unscheduled Visit falls within the next visit window, use that visit instead of documenting an unscheduled visit.

 See important information in section 6.2.5 for guidance on Unscheduled Visits after wound closure.

 "TV" = Treatment Visit

 Study Ulcer Assessments include: 1) location 2) duration 3) size 4) exudate 5) infection 6) measurement of ulcer area

 Collect pre- and post-debridement images

 Collect pre-debridement image; if performing debridement, collect post-debridement image

 Post-application image required if randomized to PriMatrix

 Image of the closed wound area to be taken

 Debride, if necessary

 If randomized to the Standard of Care cohort

 Not required for dorsal wounds; required for plantar ulcers or lateral ulcers that would benefit from offloading

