12.7. Adverse Events

Adverse Events will be coded using the MedDRA Medical Dictionary. AE's are defined as events with an onset after screening visit 1. Treatment Emergent AE's (TEAE) are defined as events with an onset on or after the randomized treatment. TEAEs will be summarized by treatment group, System Organ Class, and preferred term. The following TEAE summaries will be provided:

- TEAEs by severity grade
- TEAEs by relationship to study treatment.

In addition, separate summaries of Serious Adverse Events, and Adverse Events resulting in discontinuation of study treatment will be presented.

The safety population will be used for the safety analyses. Subjects will be counted only once for subject-based analysis. If the same event changes in severity for a subject, the worst severity will be reported.

An Adverse Event is considered treatment emergent if (1) it was not present at Screening Visit 1, and it is not a chronic condition that is part of the subject's medical history; or (2) it is present at Screening Visit 1 or as part of the subject's medical history, but the severity or frequency increases during treatment.

Treatment-emergent adverse events (TEAE) will be summarized for each treatment group by body system and preferred term. The severity of all adverse events will be determined by the investigator's judgment and classified as mild, moderate or severe.

Treatment groups will be compared with respect to the incidence of Adverse Events (all and TEAEs) and the proportion of subjects withdrawing from the study for Adverse Events by reason of withdrawal. Comparisons will be made overall, by body system and by preferred term and will be further categorized by severity and by study device relationship.

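### The protocol gives conflicting end points for collecting related non-serious AEs, and the gap falls in an interval that only healed subjects have

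*Protocol*

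**What the plan says.** Four places in the protocol bear on when collection of related, non-serious AEs stops.

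- **5.15.1 (Definitions):** "All events starting or worsening beginning at SV2 through Treatment Visit Week 13 and unscheduled visits will be collected". Section 6.2.1 uses the same style of label for the visit after randomization, "Treatment Visit Week 2, 7±3 days from Randomization/TV 1", so Treatment Visit Week 13 is TV13, nominal Day 84.
- **6.2.4 (4-Week Follow-Up Visit):** the list has three items: ulcer assessments, photograph and closure status. It has no AE item. Its opening sentence reads "The 4-week follow-up visit assessments and procedures are identified in Table 3".
- **Table 3:** the "Adverse Events" row is blank at SV1 and marked in all 17 other columns, including the one headed "4-Week 28±3d After Confirm".
- **5.15.5 (Reporting Procedures):** the investigator asks about AEs at each visit, and related AEs after the first randomized treatment are recorded. No end date is given.

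By contrast, 6.2.3 (Closure Confirmation Visit) does list the task: "Document any applicable AEs as noted by the subject or as documented in their medical record".

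On analysis, SAP 12.7 states: "Treatment groups will be compared with respect to the incidence of Adverse Events (all and TEAEs"). Neither that section nor the Fisher tests in SAP 13.2.3 take length of observation into account.

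**The concern.** A site cannot follow all four passages at once. One that works from the 6.2.4 list, or applies the 5.15.1 cut-off, will record fewer events after closure than one that works from Table 3 or 5.15.5.

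The affected interval depends on outcome. Under 3.2.3 only subjects with confirmed closure return for the 4-week visit. Under 6.2.2 subjects still open at TV13 leave the study there. The device is meant to raise the closure rate, so the arms differ by design in how many subjects have the interval. A comparison of simple AE incidence would then mix a difference in risk with a difference in observation time.

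**Working it through.** **Inputs.** Closure by week 12 is 46% Active and 26% Control, with 128 randomized per arm (Protocol 8.3). From Table 3, TVk falls on nominal Day 7(k−1), Confirmation is closure + 7 days, and the 4-week visit is closure + 35 days. Open ulcers exit at Day 84. The plan states no AE follow-up figure to reproduce.

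**1. Who has the interval.** 128 × 0.46 = 58.9 Active and 128 × 0.26 = 33.3 Control. The Active share is 0.46/(0.46 + 0.26) = 64%. It does not depend on the number per arm, so it also holds for the SAP's 120. If Control stays at 26%, the share is 50% when Active is also 26%, and 58% when Active is 36%. The 28 days average 28 × 0.46 = 12.9 days per randomized Active subject and 28 × 0.26 = 7.3 per Control subject.

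**2. Where the 4-week visit falls.** Closure at TV2 to TV8 puts it at Day 42 to 84, inside the 5.15.1 window; only the missing 6.2.4 item puts AE collection at risk. Closure at TV9 to TV13 puts it at Day 91 to 119, outside the window. Closure at TV13 also puts the Confirmation Visit (Day 91) outside it, although 6.2.3 requires AE documentation there.

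**3. Mean AE follow-up from randomization.** Assume closure is equally likely at each of TV2 to TV13 (mean Day 45.5), with no dropout. With m the mean follow-up of closers, Active = 0.54 × 84 + 0.46m and Control = 0.74 × 84 + 0.26m.

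| Reading | m (days) | Active | Control | Active vs Control |
|---|---|---|---|---|
| Ends at Confirmation (closure + 7) | 52.5 | 69.5 | 75.8 | 8.3% shorter |
| 4-week AE query made, but 5.15.1 limit applied: min(closure + 35, 84) | 71.75 | 78.4 | 80.8 | 3.0% shorter |
| Table 3 (closure + 35) | 80.5 | 82.4 | 83.1 | 0.8% shorter |

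**4. Sensitivity to closure timing.** If closures occur only at TV9 to TV13 (mean Day 70), Table 3 gives m = 105, so Active is 45.36 + 48.30 = 93.7 days and Control 62.16 + 27.30 = 89.5. Active is then followed 4.7% longer. Ending at Confirmation with the same late closures gives 80.8 vs 82.2 days (1.7% shorter).

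**5. Effect on simple incidence.** Assume an 84-day AE risk r of 20% to 40% and the same constant hazard in both arms, h = −ln(1 − r)/84. Each subject's incidence is 1 − exp(−h × follow-up), averaged over the even closure days of step 3.

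- Ending at Confirmation: 16.7% vs 18.1% at r = 20%, 25.2% vs 27.3% at r = 30%, and 33.8% vs 36.5% at r = 40%. The apparent advantage for Active is 1.4 to 2.7 points.
- Under Table 3: 0.2 to 0.4 points.

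**The case against.** The strongest reply is that little is actually lost.

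- **Infection and reopening.** A reader might infer that these go unrecorded after closure. The documents do not support that. Section 5.7.3 requires any study-ulcer infection after randomization to be recorded as an AE, with no end date, and Table 3 footnote 4 includes infection in the ulcer assessments made at the 4-week visit. Closure status is an item in 6.2.4, and 5.19 requires the investigator to document why an ulcer re-opened. What remains exposed is other related events, such as a late reaction.
- **Other routes.** Section 6.2.4 cites Table 3, 5.15.5 has AEs asked about at each visit, and AE documentation stays in force at unscheduled visits after closure (6.2.5). The loss is therefore conditional on which text a site follows. This stands, but it does not reconcile the passages.
- **The 8.3% figure.** It is tempting to present 8.3%, or 1.4 to 2.7 points, as the bias built into 5.15.1. That section does not stop at Confirmation; it runs to TV13 for everyone. With a 4-week AE query, its limit gives 3.0%.
- **Constant hazard.** Only events related to the ulcer, treatment or procedures are recorded, and dressings stop after closure (5.11). The hazard plausibly falls then, so the point differences are probably upper figures.
- **Descriptive safety analysis.** SAP 12.6 plans no inferential statistics, although 13.2.3 adds Fisher tests. Unequal observation time affects a descriptive comparison too.

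**Conclusion.** The protocol is wrong as written: 5.15.1, 5.15.5, 6.2.4 and Table 3 do not agree on when collection of related non-serious AEs ends. The consequence is modest and conditional. Some related events in the 28 days after Confirmation may be missed at some sites, among about 59 Active and 33 Control subjects at the planned rates. Those counts are subjects who have the interval, not subjects with lost events.

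Neither the size nor the direction of the follow-up imbalance is fixed. Active follow-up is 0.8% to 8.3% shorter across the three readings with even closure times, and 4.7% longer under Table 3 if closures come late. A reader might infer that adopting Table 3 would by itself remove the imbalance, but that holds only for particular closure timing. The 1.4 to 2.7 points require even closure times, collection ending at Confirmation and a constant hazard after closure.

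This point does not cover the SAE window, which 5.15.1 states separately ("All events starting or worsening after the first randomized treatment through Treatment Visit Week 12 will be collected") and which also differs from 5.15.5.

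**What to change.** 1. **Protocol.** Reconcile 5.15.1, 5.15.5, 6.2.4 and Table 3 on one end point for related AEs. Table 3 and the each-visit rule in 5.15.5 already support the last study visit. Choosing it means adding an AE item to 6.2.4, changing the end date in 5.15.1 and stating that date in 5.15.5.
2. **SAP 12.7.** Report TEAEs per subject-week of AE follow-up beside simple incidence, and define each subject's follow-up by the window actually applied. This is needed even after the wording is aligned, because AE follow-up depends on healing under every reading.
3. **If visits are already complete.** The wording change comes too late for those subjects. The SAP can still state which window sites applied and add the subject-week rate.

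The cost is one AE question at a visit already scheduled, edits to three sections and one extra column in the AE tables. A few more AEs will be recorded, mostly in Active, and the report should say so.
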